12.2.1 Baseline characteristics

Baseline characteristics will be presented with descriptive statistics.

12.2.2 Pharmacokinetics and pharmacodynamics

Listings of PD and PK blood sample collection times as well as derived sampling time deviations and in addition listings of PD (observed and change from baseline) and PK variables will be provided. Plasma concentrations and PD and PK variables will be summarized using descriptive statistics.

Plasma AMC concentrations below LLOQ will be handled as follows for descriptive statistics:

- At a time point where at least 1 value is above LLOQ but less than or equal to 50% of the values are below LLOQ, all values below LLOQ are set to LLOQ and mean (arithmetic and geometric), median, SD and CV% are calculated.
- At a time point where more than 50% of the observations are below LLOQ only individual values are reported; mean, SD, geometric mean and CV% will be set to NQ (not quantifiable). The min value and the median are set to <LLOQ.
- If all values are below LLOQ at any time point no descriptive statistics are calculated for that time point. Write NA (not applicable) in the field for SD and CV% and write <LLOQ in fields for mean, geometric mean, min, median and max in the table.
- The number of observations greater than LLOQ (n>LLOQ) will be reported in the table.

Geometric mean concentration-time profiles will be presented for both treatments on both linear and log-linear scale. Individual concentration-time data will be graphically presented on linear scale only. Linear plots ("spaghetti") of PK variables vs treatment will be displayed. The PK variables will be on the y-axis and include (if applicable): AUC, AUC_{0-last}, C_{max}, and t_{max} for AMC. The x-axis will include "clopidogrel" and "clopidogrel + esomeprazole 20 mg/ASA 81 mg". Each subject will be presented by 1 line within the graph.

Data from healthy volunteers excluded from an analysis population will be included in the data listings, but not in the summaries.

The PK variables and mIPA will be analyzed using linear mixed models (1 for each variable) with fixed effects for period and treatment and a random effect for subject within sequence. Kenward-Rogers approximation for degrees of freedom will be used. Model diagnostics such as residual plots, normality tests and Q-Q plots will be checked for all models. The results of these checks might result in different model definitions than the above or different statistical methods employed.

The mean differences between the treatments in the mIPA model will be calculated with 95% confidence interval (CI) for the differences. If deemed necessary judging by the PD variables' distribution, the PD data will analysed on log-scale and the corresponding estimates and CIs back-transformed to the original space giving true estimates of the ratios between treatments.

The ratio ((esomeprazole 20 mg/ASA 81 mg + clopidogrel)/clopidogrel) of AUC, AUC_{0-last} and $C_{ss,max}$ with corresponding 90% CI for the ratios will be calculated.

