Light transmission aggregometry is regarded as the gold standard and has been chosen for measuring platelet aggregation (PA). The absolute change in platelet reactivity when measured with light transmittance aggregometry induced by 20 μ mol/L ADP showed strong correlation with the C_{max} value of the AMC. In contrast, no significant association was observed between the C_{max} value of the AMC and inhibition of PA (IPA) using a lower concentration of 5 μ mol/L ADP, hence only the higher dose of ADP will be used (Bouman et al 2009).

The aim of this study is to assess whether there is a pharmacological interaction between esomeprazole 20 mg/ASA 81 mg and clopidogrel.

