3.2 Rationale for study design, doses and control groups

This single-center, open-label, randomized, 2-way cross-over study is designed to assess the PD and PK interaction between clopidogrel and esomeprazole 20 mg/ASA 81 mg. The crossover design improves reliability with each healthy volunteer being his/her own control by eliminating the impact of between-subject variability in the clopidogrel response.

The study will be conducted in healthy male and female volunteers to avoid interference from disease processes or other drugs. The selection criteria are defined such that subjects selected for participation in the study are known to be free from any significant illness.

Pharmacokinetic and PD sampling in each treatment period is judged to be sufficient to fulfil the objectives of the study.

The combination product esomeprazole/ASA will be developed using 2 strengths of esomeprazole (20 mg and 40 mg) and the lower strength will be used in this study. Two strengths of ASA (81 mg and 325 mg) will also be developed. For safety reasons, only the lower strength of ASA, 81 mg, will be used in this study. The recommended maintenance dose of clopidogrel, 75 mg, will be administered.

Clopidogrel will be administered for 9 days in order to reach steady-state conditions (steady state is reached between Day 3 and Day 7 (Plavix® Prescribing Information). A 5 day co-administration of esomeprazole 20 mg/ASA 81 mg is chosen to ensure steady-state of esomeprazole and to ensure full potential inhibition.

Due to irreversible binding with AMC, platelets are affected for the remainder of their lifespan (approximately 7 to 10 days) and recovery of normal platelet function occurs at a rate consistent with platelet turnover. The washout period of 14 days will ensure complete platelet turnover between treatment periods.

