11. EVALUATION AND CALCULATION OF VARIABLES

In all analyses, change from baseline will be calculated as the post-baseline value minus the baseline value, where baseline is defined as the last non-missing value before first administration of IP in each treatment period.

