11.4 Calculation or derivation of pharmacodynamic variable(s)

Analysis of the PD of clopidogrel will be the responsibility of the study biostatistician at Quintiles, Global Phase I Services, Uppsala, Sweden. Quintiles SOPs and WIs will be used as the default methodology if not otherwise specified.

The primary PD variable is mIPA which will be based on mPA to 20 µmol/L ADP assessed at baseline (Day -1 for Period 1 and pre-dose on Day 1 for Period 2) and 24 h after dose on Day 9. If data permits, mIPA will be calculated as:

mIPA $[1 - (postdose mPA) on Day 9)/(mPA at baseline)] \times 100$

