12.3 Determination of sample size

The study is sized to estimate the absolute mean difference in IPA with and without the PPI with a specified precision. With 54 healthy volunteers, a 95% CI with length of at most 9 percentage units is achieved with at least 96% probability. With a projected dropout rate of 10%, a total of 59 healthy volunteers will be randomized.

The calculation assumes a SD of paired difference of 14% units, derived from the root mean square error of the analysis of internal data on ADP-induced maximum extent IPA for $^{\circ}$ IPA_{max} (20 μ mol/L).

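### The primary mIPA model uses each period's baseline mPA only as a divisor, so the 95% CI may be wider than necessary; a pre-specified baseline term would cost about 1% of its length at worst

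*Protocol*

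**What the plan says.** Section 12.2.2, repeated in the synopsis, fixes one linear mixed model per variable with "fixed effects for period and treatment and a random effect for subject within sequence". The mean treatment difference in mIPA is reported with a 95% CI. No baseline covariate is named. The section allows the model to change after residual diagnostics, but does not mention baseline there either.

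Section 11.4 defines mIPA as 100 times one minus the ratio "postdose mPA) on Day 9)/(mPA at baseline". The readings are taken at "Day -1 for Period 1 and pre-dose on Day 1 for Period 2) and 24 h after dose on Day 9". Section 11 makes the baseline period-specific, "where baseline is defined as the last non-missing value before first administration of IP in each treatment period". Each volunteer thus has two off-drug baselines, one per period. Section 3.2 treats the second as fully recovered: "The washout period of 14 days will ensure complete platelet turnover between treatment periods".

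Section 12.3 justifies the sample size by CI length alone: with 54 volunteers, "a 95% CI with length of at most 9 percentage units is achieved with at least 96% probability", assuming an SD of the paired difference of 14 percentage units. It randomizes 59 to allow for 10% dropout.

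**The concern.** If section 3.2 is right, the two baselines of one volunteer measure the same untreated state. A difference between them is then mostly reading error or day-to-day variation, apart from any shift common to all volunteers. The subject effect removes a volunteer's stable level and the period effect removes a common shift. Neither removes the individual deviation between the two readings.

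Dividing by baseline imposes a fixed proportional relation instead of estimating one. If a volunteer's baseline is high by chance in one period and the Day 9 reading does not move with it, mIPA in that period is inflated, and the error passes into the paired difference. A baseline covariate would take out that part. Because the study is sized on CI length only, a measurement already collected that could shorten the interval bears directly on the design goal.

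**Working it through.** **Inputs from the protocol.** SD of paired difference 14, target CI length at most 9, 54 evaluable, 59 randomized, 10% dropout (section 12.3); model terms (section 12.2.2); mIPA formula (section 11.4). Completers: 59 x 0.9 = 53.1, taken as 53.

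**Assumed, because the protocol gives no value.** Mean mIPA 45; within-subject baseline CV *c* of 3% to 10%; correlation *r* of 0, 0.3 or 0.5 between the baseline error and the Day 9 error within a period.

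**Step 1: reproduce the stated precision.** CI length = 2 x t(0.975, df) x s / sqrt(n), so P(length <= 9) = P(chi-square on df <= df x [9 sqrt(n) / (2 t x 14)]^2).
- n = 54, df = 52: length at s = 14 is 7.65 and the probability is 0.966. The stated figure of at least 96% reproduces.
- n = 53, df = 51: length at s = 14 is 7.72 and the probability is 0.955. Since the expected sample SD is slightly below 14, the mean length is about 7.68.

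**Step 2: how baseline error enters.** To first order, a baseline error of CV *c* shifts mIPA by a = c x (1 - 0.45), that is 0.55 points per 1% of CV. Let p be the Day 9 error in mIPA points. Two periods enter each paired difference, so

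2 (a^2 + p^2 - 2 r a p) = 14^2, or a^2 + p^2 - 2 r a p = 98.

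Solving, p = r a + sqrt(98 - a^2 (1 - r^2)).

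**Step 3: adjust.** Regressing on the within-volunteer baseline difference leaves p^2 (1 - r^2) in place of 98. The covariate costs t(50)/t(51) x sqrt(51/50) = 1.010. Length ratio = 1.010 x sqrt(p^2 (1 - r^2) / 98).

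Example, c = 10%, r = 0: a = 5.5, p^2 = 98 - 30.25 = 67.75, ratio = 1.010 x sqrt(67.75/98) = 0.840, so the mean length falls from 7.68 to about 6.45.

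Change in CI length:

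| Baseline CV | r = 0 | r = 0.3 | r = 0.5 |
|---|---|---|---|
| 3% | -0.4% | 0.0% | -6.1% |
| 5% | -2.9% | +1.0% | -2.9% |
| 8% | -9.5% | +0.1% | +0.2% |
| 10% | -16.0% | -2.2% | +1.0% |

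**Step 4: break-even and worst case.** Let rho be the correlation between the baseline difference and the mIPA difference. The covariate pays for itself once 1.010 x sqrt(1 - rho^2) < 1, that is, rho above about 0.14. If rho is zero (the baseline deviation fully and proportionally shared with Day 9), the CI is about 1% longer and P(length <= 9) at 53 completers falls from 0.955 to about 0.94.

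**Step 5: simulation check.** A 2x2 crossover of 54 volunteers was simulated with the actual ratio, the paired SD held near 14, assumed mean baseline mPA 80, within-subject baseline SD 3 to 8 points and mean mIPA 30 to 60. CI length changed by -0.2% to -31% when the baseline deviation was not shared with Day 9 (-5.5% at SD 5 and mIPA 45), by +0.7% to -6% when half was shared, and by about +1% when all was shared. Coverage was about 95% with and without the covariate.

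**The case against.** The strongest reply is that nothing here is an error. Period, treatment and subject within sequence is a standard and valid model for a two-period crossover, and the stated precision is met without a covariate. This stands. So does the point that mIPA is already relative to baseline, as the primary objective asks. If a volunteer's platelet reactivity truly differs between periods and the difference persists to Day 9, the within-period ratio cancels it, and a covariate only spends a degree of freedom. It also stands that the 14 comes from an earlier analysis whose handling of baseline is not described.

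The large gains do depend on favourable inputs: -16% needs a CV of 10% and independent errors, and at correlation 0.3 most of the gain is gone. What the reply does not remove is the asymmetry between a cost of about 1% and a possible gain several times that.

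Three stronger readings are tempting, and the documents do not support them.
- A reader might infer that the CI is certainly too wide. That depends on a correlation the protocol does not give.
- A reader might infer that adjustment corrects for incomplete platelet recovery at the Period 2 baseline. Section 3.2 asserts complete turnover; a recovery loss equal in both sequences goes largely into the period effect; and a treatment-dependent loss would be corrected only if Day 9 were unaffected by it.
- A reader might take section 1.2, "The absolute change in platelet reactivity when measured with light transmittance aggregometry", as evidence against a ratio. That passage supports the choice of 20 over 5 umol/L ADP and does not compare ways of using the baseline.

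**Conclusion.** The point holds as one of efficiency. The model leaves in the treatment difference whatever part of the baseline deviation Day 9 does not share proportionally, so the 95% CI may be wider than necessary. There is no bias, and the sample-size statement is not wrong. With 53 completers, SD 14 and an assumed mean mIPA of 45, the change in CI length from adjusting lies between about 1% longer and 16% shorter for baseline CVs of 3% to 10%, depending on an error correlation that must be assumed. A lower mean mIPA would enlarge the possible gain, and a higher one would shrink it.

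The timing argues for settling this beforehand. Section 12.2.2 lets diagnostics change the model, and a baseline term added after the data are seen in an open-label study would be a data-driven change to the primary analysis.

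**What to change.** In section 12.2.2, pre-specify baseline mPA in the mIPA mixed model as two fixed covariates: the volunteer's mean of the two baselines, and the period's deviation from that mean. The split matters because a single period-baseline term in a random-subject model mixes the between- and within-volunteer slopes. Report the adjusted B minus A mean difference with its 95% CI as primary, and keep the current unadjusted model as supportive. Make the same change in the synopsis.

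The definition of mIPA, the sampling schedule and the number of volunteers do not change. The cost is a sentence of text and one or two degrees of freedom, that is, a CI about 1% longer if baseline proves uninformative. If internal aggregometry data give the within-subject baseline CV and its correlation with on-treatment readings, the sponsor can check before finalizing whether the gain is likely to exceed that.

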12.2.3 Pharmacogenetics

Listings of CYP2C19 alleles and metabolic status will be provided. Subpopulation analysis of selected PD and/or PK variables by CYP2C19 genotype may be performed if found necessary and if data allows.

12.2.4 Safety

Continuous variables will be summarized using descriptive statistics by treatment. Categorical variables will be summarized in frequency tables (frequency and percentage) by treatment

For qualitative variables, the sample size (N), the number of available data (n) and the percentage (of available data) for each class of the variable will be presented.

Adverse events will be summarized by treatment by preferred term and system organ class using MedDRA vocabulary. Furthermore, listings of SAEs and AEs that led to withdrawal will be made and the number of volunteers who had any AEs, SAEs, AEs that led to withdrawal and AEs with severe intensity will be summarized.

In tables (and figures if any), AEs will be summarized by treatment and washout periods. The washout periods will be defined as "Washout Clopidogrel" and "Washout Esomeprazole 20 mg/ASA 81 mg " on an individual level depending on the preceding treatment. The washout periods ends at the first drug administration in the following treatment period or, in case of the washout after the last treatment period, at the end of study for the subject (follow-up). The washout periods are considered to start 24 h after the dose on Day 9 (ie, on Day 10) in the treatment periods.

Tabulations and listings of data for vital signs, clinical laboratory tests and physical examination findings parameters will be presented. A listing of screening pECG data will be presented. Where applicable, data will be summarized for the absolute value at each scheduled assessment, together with the corresponding changes from the baseline. For clinical laboratory tests, listings of values for each volunteer will be presented with abnormal or out-of-range values flagged.

For the purpose of tabulations and graphical presentations of safety laboratory data, if several measurements have been taken for the same subject, protocol time point and laboratory variable, the last non-missing value will used if taken before first administration of IP. Otherwise, the first non-missing value will be used.

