2.2 Secondary objectives

- To assess the effect of esomeprazole 20 mg/ASA 81 mg on the pharmacokinetics (PK) of AMC by assessing AUC, AUC_{0-last} and C_{ss,max} of AMC on Day 9
- To assess the safety and tolerability of clopidogrel given alone and concomitantly with esomeprazole 20 mg/ASA 81 mg by assessing adverse events (AEs), vital signs, laboratory variables, electrocardiogram (ECG) and physical examination

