3.1 Overall study design and flow chart

The study will be performed at Quintiles AB, Uppsala, Sweden. This is an open-label, randomized, 2-way cross-over study designed to assess the PD and PK interaction between clopidogrel and esomeprazole 20 mg/ASA 81 mg. Fifty-nine (59) healthy male and female volunteers will be enrolled and randomized to treatment.

The total study duration for each healthy volunteer is approximately 2.5 months. This includes a pre-entry visit within 28 days prior to randomization, 2 treatment periods of 9 days, washout periods of at least 14 days between the treatment periods (ie, between the last dose in period 1 and the first dose in period 2) and a follow-up visit 7 to 10 days after the last dose. See Figure 1.

In each treatment period, the healthy volunteers will arrive at the study unit on Day -1 and start treatment on Day 1. For treatment A, the healthy volunteers will take the subsequent doses on Days 2 to 8 at home and receive the dose on Day 9 at the study unit (they will return to the study unit in the evening of Day 8). For treatment B, the healthy volunteers will take the subsequent doses on Days 2 to 4 at home and they will return to the study unit to receive the doses on Days 5 to 9.

Figure 1 Study flow chart

- a Healthy volunteers will be administered the following treatments in randomized order (see Section 5.5.2) in Period 1 and 2:
 - Treatment A: clopidogrel 75 mg once daily for 9 days
 - Treatment B: clopidogrel 75 mg once daily for 4 days followed by esomeprazole 20 mg/ASA 81 mg with clopidogrel 75 mg once daily for 5 days
- b Investigational product (IP, esomeprazole 20 mg/ASA 81 mg and clopidogrel)
- c The washout period will be at least 14 days between the last dose in period 1 and the first dose in period 2.

Healthy volunteers will be administered IP for 9 days. Blood sampling for PD assessment will be drawn on Day -1 (Period 1)/pre-dose on Day 1 (Period 2) as baseline and 24 h after dose on Day 9. Blood samples for determination of AMC will be drawn pre-dose and 0.25, 0.5, 1, 1.5, 2, 3, 4, 6, 8, 10 and 12 h after the last dose on Day 9. Safety monitoring will be performed during the treatment periods. Standardized food will be served during the residential periods. The study plan and study time schedule are found in Table 1 and Table 2, respectively.

A genetic sample will be taken to assess CYP2C19 status on Day -1 in Period 1, once the informed consent has been signed.

Table 1 Study plan

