5.5.2 Doses and treatment regimens

This study has 2 treatment arms and 2 treatment periods separated by a washout period of at least 14 days. All study medications will be administered via the oral route. Each volunteer will receive 2 treatments in randomized order (see Section 5.2.1):

- Treatment A: clopidogrel 75 mg once daily for 9 days
- Treatment B: clopidogrel 75 mg for 4 days followed by esomeprazole 20 mg/ASA 81 mg with clopidogrel 75 mg once daily for 5 days

For treatment A, the healthy volunteers will receive the first dose of clopidogrel at the study unit on Day 1, take the subsequent doses on Days 2 to 8 at home and at the study unit on Day 9. For treatment B, the healthy volunteers will receive the first dose of clopidogrel at the study unit on Day 1, take the subsequent doses on Days 2 to 4 at home and at the study unit on Days 5 to 9.

At the study unit, IPs will be administered with approximately 240 mL of water. The capsules/tablets must not be chewed, crushed or divided, but should be swallowed whole. The healthy volunteers will be instructed to have the same dosing procedures (including at approximately the same time) at home.

On Day 9, IP will be administered following a fast of at least 10 h (moderate amounts of water will be allowed until 1 h before dosing) and volunteers will continue to fast for 1 h after dosing. Healthy volunteers will be in an upright position (upper part of the body erect at least 45 degrees from horizontal) at the time of IP administration and will be asked to remain in an upright position for at least 1 h following IP administration.

Healthy volunteers will be instructed to record the date and time of each dose taken at home of IP in a medication log and instructed to return the medication log at the next visit to the study unit. The healthy volunteers will be instructed to, if they forgets to take a dose of IP, take the missed dose as soon as possible if it is less than or equal to 12 h since the dose was missed or to skip that dose and wait to take the next scheduled dose if it has been longer than 12 h since the dose was missed.

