6.3.3 Recording of adverse events

Time period for collection of adverse events

Adverse events will be collected from the first administration of IP throughout the study, including the follow-up visit.

Serious AEs will be recorded from the time of informed consent throughout the study, including the follow-up visit.

Follow-up of unresolved adverse events

Any AEs that are unresolved at the healthy volunteer's last visit in the study are followed up by the investigator for as long as medically indicated, but without further recording in the CRF. AstraZeneca retains the right to request additional information for any healthy volunteer with ongoing AE(s)/SAE(s) at the end of the study, if judged necessary.

Variables

The following variables will be recorded for each AE;

- AE (verbatim)
- The date and time when the AE started and stopped
- Maximum intensity on a scale of 1 to 3:
 - 1. mild (awareness of sign or symptom, but easily tolerated)
 - 2. moderate (discomfort sufficient to cause interference with normal activities)
 - 3. severe (incapacitating, with inability to perform normal activities)
- Whether the AE is serious or not
- Investigator causality rating against the IP (yes or no)
- Action taken with regard to IP
- AE caused healthy volunteer's withdrawal from study (yes or no)
- Outcome

In addition, the following variables will be collected for SAEs:

- Date AE met criteria for serious AE
- Date Investigator became aware of serious AE
- AE is serious due to
- Date of hospitalization
- Date of discharge
- Probable cause of death
- Date of death

- Autopsy performed
- Causality assessment in relation to study procedure(s)
- Causality assessment in relation to other medication
- Description of AE

It is important to distinguish between serious and severe AEs. Severity is a measure of intensity whereas seriousness is defined by the criteria in Section 6.3.2. An AE of severe intensity need not necessarily be considered serious. For example, nausea that persists for several hours may be considered severe nausea, but not an SAE. On the other hand, a stroke that results in only a limited degree of disability may be considered a mild stroke but would be an SAE.

Causality collection

The Investigator will assess causal relationship between IP and each AE, and answer 'yes' or 'no' to the question 'Do you consider that there is a reasonable possibility that the event may have been caused by the IP?'.

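### AE tables by treatment have no boundary at the Day 5 dose, so clopidogrel-only events on Days 1-4 of Treatment B are counted under the combination

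*Protocol*

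**What the plan says.** Section 5.5.2 defines two regimens, each of nine days: "Treatment A: clopidogrel 75 mg once daily for 9 days" and "Treatment B: clopidogrel 75 mg for 4 days followed by esomeprazole 20 mg/ASA 81 mg with clopidogrel 75 mg once daily for 5 days". It treats each regimen as one treatment: "Each volunteer will receive 2 treatments in randomized order". Section 3.1 describes B in the same way.

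Section 12.2.4 takes these treatments as the unit of tabulation: "Adverse events will be summarized by treatment by preferred term and system organ class using MedDRA vocabulary", and "In tables (and figures if any), AEs will be summarized by treatment and washout periods". It places the end of a washout at the first drug administration of the next treatment period, and its start 24 h after the Day 9 dose. It also names the washout that follows B after the combination product.

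The safety objective in section 2.2 is worded by exposure, not by regimen: "To assess the safety and tolerability of clopidogrel given alone and concomitantly with esomeprazole 20 mg/ASA 81 mg".

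Section 6.3.3 lists among the variables recorded for each AE: "The date and time when the AE started and stopped".

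**The concern.** The objective contrasts clopidogrel alone with clopidogrel plus esomeprazole/ASA. The first four days of B are clopidogrel alone, identical in drug intake to the first four days of A, yet nothing in section 12.2.4 separates them from the five days on the combination. A reader of the tables will take the B column as experience on the combination.

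Two things are at stake. The first is attribution. The safety analysis set (section 12.1.4) requires only one dose of any investigational product and some post-dose data. A volunteer who withdraws for an AE on Day 3 of B would therefore appear under B as a withdrawal due to an AE without having taken esomeprazole/ASA. The second is contrast. Section 1.3 names bleeding as the risk of clopidogrel and refers to observation in the unit when it is given with the combination. Four days of identical treatment in both columns make a relative difference that arises from Day 5 look smaller.

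**Working it through.** The plan states no figure on this point, so there is none to reproduce. The check has two parts.

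**1. Which column does an AE on Days 1-4 of B fall into?**
- Start of the treatment window: the preceding washout ends at the first drug administration of the period, which is the Day 1 dose.
- End of the window: the following washout starts 24 h after the Day 9 dose, on Day 10.
- Between these edges section 12.2.4 sets no further boundary, and sections 3.1 and 5.5.2 call the whole nine days Treatment B.
- The as-treated rule in section 12.1.1 does not help. It concerns volunteers who receive a treatment other than the one assigned, and a volunteer on Day 3 of B is receiving B as assigned.

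Such an AE is therefore counted under B. By dosing days, 4/9 = 44% of the B window precedes any combination dose.

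**2. How much does this change the comparison?**

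The protocol gives no AE rates, so the following are assumptions: a constant daily AE rate L on clopidogrel alone and R × L on the combination, with a nine-day clopidogrel-alone risk p of 10% to 50%.

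*Event-rate ratio, whole period:* (4 + 5R)/9.
- R = 1.5: 11.5/9 = 1.28
- R = 2: 14/9 = 1.56
- R = 3: 19/9 = 2.11

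*Difference in expected event counts:* (4 + 5R)L − 9L = 5L(R − 1). On Days 5-9 alone it is 5RL − 5L = 5L(R − 1). The two are equal, so there is no bias; Days 1-4 add only noise.

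*Share of volunteers with any AE:* 1 − exp(−rate × days). With p = 20% and R = 2:

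| Window | A | B | Difference | Ratio |
|---|---|---|---|---|
| Whole period | 20.0% | 1 − 0.8^(14/9) = 29.3% | 9.3 points | 1.47 |
| Day 5 dose to Day 10 | 1 − 0.8^(5/9) = 11.7% | 1 − 0.8^(10/9) = 22.0% | 10.3 points | 1.88 |

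In general the whole-period risk difference equals the Days 5-9 difference multiplied by the probability of no AE on Days 1-4, (1 − p)^(4/9):
- p = 10%: 0.95
- p = 20%: 0.91
- p = 30%: 0.85
- p = 50%: 0.74

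Over p of 10% to 50% and R of 1.5 to 3, the whole-period risk ratios are 1.18 to 1.99, against 1.37 to 2.83 for Days 5-9.

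**3. Would pooling all clopidogrel-alone time do instead?**

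Combining all of A with Days 1-4 of B sets 9 + 4 = 13 days against 5. With p = 20% and R = 2, the share with any AE would be 1 − 0.8^(13/9) = 27.6% on clopidogrel alone and 22.0% on the combination. A true doubling would look like fewer AEs. Unadjusted pooling is worse than the present plan.

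**The case against.** The strongest reply has four parts.

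*The assignment is inferred, and an SAP may split the window.* No sentence says that Days 1-4 of B count as the combination, and AE sub-windows are often left to the SAP. But the protocol is not silent here. It fixes the edges of the AE windows, in one case to the hour, and leaves out the one boundary that separates the two exposures. The inference follows from its own definitions, and an SAP could refine it.

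*The whole-period table is a legitimate summary.* Comparing two randomized nine-day regimens of equal length within subject is standard for a crossover and answers what happens under each regimen. That stands, and it is why the table should be kept. It does not answer the objective as worded in section 2.2.

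*The dilution is smaller than it looks.* A reader might infer from (4 + 5R)/9 that the planned tables report a ratio diluted by that amount, or that any true excess is pulled towards no difference on every scale. The documents do not support this. Section 12.2.4 plans frequencies, percentages and numbers of volunteers, and the synopsis calls the safety presentation descriptive; no AE ratio, interval or test is planned. On the count scale there is no bias, and on the risk-difference scale the loss is modest when AEs are uncommon. This part of the reply stands in full.

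*The Days 5-9 window is not clean.* Under section 3.1, volunteers on B are in the study unit for Days 5-9, while those on A are at home until the evening of Day 8. In an open-label study, ascertainment may differ. That stands as a caution. The same imbalance already sits inside the whole-period tables, so splitting reveals it and does not create it.

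**Conclusion.** The point holds as a mismatch between the AE windows in section 12.2.4 and the exposure contrast in section 2.2. AEs with onset before any esomeprazole/ASA are tabulated under the combination. That conclusion rests on the protocol's definitions and needs no assumption about rates.

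The numerical effect does rest on the assumed constant daily rate. It is clear on the ratio scale (2 shown as 1.56), modest on the difference in the share of volunteers with any AE (9.3 instead of 10.3 points in the example) and absent for the difference in expected counts. A reader might take the 44% to mean that nearly half of the AEs reported under B are misattributed. It is a share of dosing days; the share of events depends on rates that the protocol does not give, and at R = 2 it would be 4/14 = 29%.

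No test or error rate is involved, and the primary pharmacodynamic and the pharmacokinetic analyses are untouched. This is a cheap improvement to a descriptive secondary objective.

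**What to change.** In section 12.2.4:
- Add a boundary at the Day 5 dose and assign each AE by its recorded onset date and time.
- Make the main AE comparison events with onset from the Day 5 dose to 24 h after the Day 9 dose in B, against the same window in A. Length and study day then match.
- Show Days 1-4 as a separate column for each treatment.
- Do not pool A with Days 1-4 of B unless exposure time is adjusted for.
- Keep the whole-period tables as supportive.
- Add a note that on Days 5-9 volunteers on B are resident while those on A are at home until the evening of Day 8, so AE ascertainment may differ.

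The cost is one paragraph of text, some extra table programming and fewer events per table. No new data or study procedure is needed.
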